## **Abstract**

**Background:** This study argues that providing evidence-based occupational therapy patient education is vital in order to optimize rehabilitation outcomes. The planned trial aims to evaluate the SADL-eM intervention for people with SCI compared with standard treatment.

**Methods/Design:** This is a parallel randomized clinical trial with two study arms, intervention and control. Ninety patients treated in inpatient rehabilitation settings will be randomly allocated to two study groups. Both groups will receive standard care. The intervention group will also receive a copy of the SADL-eM from their treating occupational therapist during an individual session. Assessment on admission (baseline measure) and after six weeks of admission will use the SCIM-SR as the primary outcome measure. Secondary outcomes include the SCIM-III, Private Religiousness Practices Scale, Organizational Religiousness Short-Form, additional domains of ADL covered by the educational manual and adherence to intervention. Effect will be determined using repeated measures ANOVA.

**Discussion:** The SADL-eM is a comprehensive ADL educational tool that aims to optimize rehabilitation outcomes for people with SCI. If the SADL-eM is demonstrated as clinically effective, this will have significant implications for occupational therapy interventions in LMIC settings.

**Trial registration:** BLINDED FOR REVIEW (Project ID: 1635, HREC Reference number: S17/10/206). Helsinki Committee for Ethical Approval (PHRC/HC/689/20)

**Date of registration:** 30/11/2017, Renewed 12/06/2020

**Keywords:** Occupational therapy, educational intervention, Activities of daily living, Spinal Cord Injury, clinical trials

## Introduction

Patient education is gaining more interest especially during the time of COVID-19 (Wasson, 2020). People with SCIs requiring inpatient rehabilitation in the Gaza Strip complete their medical management in a secondary healthcare facility and arrange for subsequent referral and admission to an inpatient rehabilitation setting. Due to limited resources, many patients are added to waiting list before admission. Providing functional therapy and health education as the main objectives of inpatient rehabilitation for people with spinal cord injury in Low and Middle Income Countries (LMIC) is being limited by shorter length of stay (LOS) in inpatient rehabilitation settings and inadequate community rehabilitation. Some inpatients are being discharged home with less skills in Activities of Daily Living (ADL), mobility, and prevention of medical complications. These challenges increase the demand for evidence based educational interventions including ADL education during inpatient care, that improves rehabilitation outcomes ([name], [name], and [name], 2019).

SCI patient education aims to develop knowledge, skills, attitudes, and behaviors to maintain health and wellbeing, prevent secondary complications, and enhance active life participation ([name], et al., 2019). Topics presented early in the admission phase may include body anatomy and functioning, while others like community integration can be presented at later phases of rehabilitation so that SCI individuals will become progressively independent in activities of daily living (Letts et al., 2011).

An effective SCI educational manual should be accessible and motivating in terms of information, details, and layout. It should provide support, for example web groups, consultations, and answers to common questions. An SCI educational manual must also be cost-effective, up-to-date and meet the needs of people from different backgrounds, preferences, genders and ethnicities (Chou, et al., 2012). It is important that SCI educational manuals targeting adults provide autonomy and are guided by adult learning theory to facilitate active roles of people with SCI (May, Day, and Warren, 2006). Staff availability (time allocated

for patient education) and patient readiness (motivation and interest) are two important concerns for effective patient education. Time allocated for patient education can be limited and inadequate due to patient treatment workload and staffing shortages. Decreased motivation and interest of the patient during rehabilitation adds another barrier to patient education (Shepherd, et al., 2012).

This study plans to evaluate the impact of providing an evidence-informed SCI ADL educational manual (SADL-eM) on activities of daily living among people undergoing rehabilitation for a spinal cord injury in the Gaza Strip, Palestine. This study may counter the effect of decreased LOS in rehabilitation in this LMIC context. By improving patient education, the authors intend to improve patients' involvement in their treatment during their stay in the three inpatient rehabilitation settings available in the Gaza Strip. An effective educational intervention will enhance the quality of care and reduce the cost of healthcare services in the long term.

This aim of the proposed study is to evaluate the impact of a SADL-eM on activities of daily living. This educational intervention is delivered to inpatients with SCI in a rehabilitation setting.

### **Research question**

Does the implementation of a SADL-eM delivered to SCI patients in an inpatient rehabilitation setting in the Gaza Strip have a significant impact on activities of daily living?

### **Primary objectives**

- a. To describe the characteristics of the participants (people with SCI in the Gaza Strip using the Biographical Data Form developed for this study).
- b. To compare the effect of the educational manual, relative to usual care, on self-reported changes in activities of daily living from admission to 6-weeks post-admission, using the SCIM-SR patient-rated measure.
- c. To compare the effect of the educational manual, relative to usual care, on observed changes in activities of daily living from admission to 6-weeks post-admission, using the SCIM-III clinician-rated measure.
- d. To compare the effect of the education manual, relative to usual care, on religious practice using the Private Religiousness Practices Scale and Organizational Religiousness Short-Form.

- e. To compare the effect of the education manual, relative to usual care, on the domains of ADL covered by the education manual including driving and community mobility, personal device care, health management and maintenance, Wudu, and Salat, using questions developed for this research.

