### **Research Hypothesis**

- a. **Null hypothesis:** There is no difference between the SADL-eM and the standard care delivered to inpatients with SCI in a rehabilitation setting.
- b. **Alternative hypothesis:** The implementation of a SADL-eM delivered to inpatients with SCI in a rehabilitation setting has a significant impact on their ADL.

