## **Data Analysis**

Captured data will be coded and reviewed by the researchers for clarity and completion. A spread sheet will be prepared by the three researchers and then loaded to IBMSPSS 21 for analysis. The first author will perform data entry. The research assistant will check the data entry using the original forms, and the research supervisor will check the data for missing data and entry errors.

The following statistical methods will be used to test the research hypothesis:

- a. To describe participants' characteristics: descriptive statistics such as frequency, percentage, mean with standard deviation for Normally distributed data and median and Inter Quartile range will be used for continuous variables that are not Normally distributed will be used.
- b. Missing values will not be substituted. Intention-to treat analysis method will be used for analysis.
- c. To determine the significance of biographical variables at baseline: McNemar and Chi Square with Nominal variables, T-test and Mann-Whitney for interval variables will be used.
- d. To compare the efficacy of the educational manual: Repeated Measures ANOVA/ Linear Mixed Models will be used will be used to assess differences between intervention and control group using the ADL data. The Repeated Measures ANOVA and Linear Mixed Models will be used to analyze the data. Linear Mixed Models has advantage in dealing with missing values and provides fixed and random effect (Krueger and Tian, 2004).
- e. Adherence to the intervention will be summarized using frequency and percentage.

All the data collected and entered (hardcopy and soft copy) will be securely stored by the first researcher in a locked cabinet on hospital premises (hardcopy) and in a password-protected file online.

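### SCIM-SR is named as primary only in the Abstract; the objectives, hypothesis and analysis leave up to nine measures open to carry one ADL claim, with no testing rule

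*Combined protocol and SAP*

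**What the plan says.** The Abstract ranks the outcomes. The trial "will use the SCIM-SR as the primary outcome measure", and "Secondary outcomes include the SCIM-III, Private Religiousness Practices Scale, Organizational Religiousness Short-Form, additional domains of ADL covered by the educational manual" follow, together with adherence.

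The Primary objectives section groups them differently. After a descriptive objective (a), it lists four comparisons with usual care:

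- b: the effect "on self-reported changes in activities of daily living from admission to 6-weeks post-admission, using the SCIM-SR patient-rated measure"
- c: the effect "on observed changes in activities of daily living from admission to 6-weeks post-admission, using the SCIM-III clinician-rated measure"
- d: the effect "on religious practice using the Private Religiousness Practices Scale and Organizational Religiousness Short-Form"
- e: the effect on the ADL domains that the manual covers, with five named

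The Secondary objectives section keeps only biographical predictors (f) and adherence (g).

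The Research Hypothesis section has one null hypothesis, with no outcome named, and one alternative: that the manual "has a significant impact on their ADL". In Data Analysis, item d says that repeated measures ANOVA or linear mixed models "will be used to assess differences between intervention and control group using the ADL data". Data Collection lists SCIM-SR, SCIM-III, both religiousness scales and the five domains under the collection of ADL data, and assigns those data to the group comparison and the hypothesis test. No section gives an order of testing, a split of alpha or a multiplicity adjustment. The sample-size paragraph does not say which outcome it was computed for.

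**The concern.** The trial has one confirmatory claim, about ADL. The Abstract ties it to SCIM-SR, but the sections that would carry that choice into the analysis do not. An analyst working from the objectives, hypothesis and analysis text could not tell which result decides the trial.

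This matters because the measures may disagree. The design is assessor-blinded; SCIM-SR is completed by the patient and SCIM-III is administered by the research assistant. If one favours the manual and the other does not, the body of the protocol does not say which governs. A choice made after the results are known would not hold the 5% error rate, and later wording could not restore it.

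**Working it through.** **1. The plan's own figure.** The plan states 90 patients (45 per arm) for an effect size of 15%, 80% power and 5% error. It does not state the effect-size metric or the correlation between the two assessments. Assume that 15% means Cohen's f = 0.15 and that the correlation is 0.5. For the group-by-time interaction with m = 2 assessments:

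- Noncentrality = N × f² × m / (1 − rho) = 90 × 0.0225 × 2 / 0.5 = 8.1, with 1 and 88 degrees of freedom.
- Power at a single 5% test = 0.804, and 90 is the smallest even total that reaches 80%.
- With rho = 0.3 the total would be 126, and with rho = 0.7 it would be 56.

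On these assumptions, 90 is the size for one test at 5%, with no allowance for further tests.

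**2. Counting the measures under Primary objectives.** SCIM-SR (1) + SCIM-III (1) + religiousness scales (2) + named ADL domains (5) = 9. The list in objective e is worded as open-ended. The plan does not say whether its domains are tested separately.

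**3. Chance of at least one false positive if any measure could support the claim.** For k independent tests at 5% this is 1 − 0.95^k:

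- k = 9: 1 − 0.95^9 = 0.370
- k = 7 (religiousness scales left out): 1 − 0.95^7 = 0.302
- k = 4 (one test for each of objectives b to e): 1 − 0.95^4 = 0.185
- k = 1 (SCIM-SR only): 0.05

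**4. Allowing for correlation.** The documents give no correlation across all nine measures, so a range is needed. These are simulated two-sided 5% tests with equal correlation r (400,000 draws, k = 9):

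| r | At least one false positive |
|---|---|
| 0 | 0.370 |
| 0.3 | 0.327 |
| 0.5 | 0.270 |
| 0.7 | 0.202 |
| 0.9 | 0.124 |

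For SCIM-SR and SCIM-III alone, the figure is 0.0975 if independent and about 0.083 at r = 0.7.

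**5. Cost of keeping several measures primary.** This uses the assumptions of step 1 and a Bonferroni split:

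- Nine measures: 0.05 / 9 = 0.0056 each. Power at 90 patients falls to 0.50, and about 150 patients are needed for 80%.
- SCIM-SR and SCIM-III only: 0.025 each. Power at 90 is 0.71, and 110 patients are needed.
- SCIM-SR alone: 0.05, with 90 patients as planned.

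**The case against.** The strongest reply is that a primary outcome is on record. The Abstract names SCIM-SR, and no section designates a rival. The Primary objectives section lists aims, and its first item is purely descriptive, so its heading cannot be a list of confirmatory tests. On that reading SCIM-SR is tested at 5% and there is no inflation. This stands as a possible reading, and it is why the 5% case belongs in the range. It does not close the matter, because the objectives, hypothesis and analysis sections do not carry the Abstract's ranking forward.

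A reader might infer that the plan allows a win on any one measure. It does not say so. The defect is that there is no decision rule, so such a claim is not excluded.

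A reader might also take 37% as the trial's error rate. It is a ceiling that needs independence and separate testing of every domain. Independence is implausible for the two SCIM versions: the protocol's description of SCIM-SR reports validity coefficients against SCIM-III above 0.7. Those coefficients concern scores rather than changes, so r = 0.7 for that pair is only illustrative.

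Whether the religiousness scales bear on an ADL hypothesis is unsettled. Objective d speaks of religious practice, while Data Collection files the scales with the ADL data.

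Finally, it is tempting to argue that religious attendance or driving can hardly change during the inpatient stay. The documents do not say this, and the point does not need it.

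**Conclusion.** The inconsistency is documented and should be removed before analysis. The Abstract's single primary outcome is not carried into the sections that define the claim and its test, and no multiplicity rule fills the gap.

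The size depends on which reading governs. It is 5% if SCIM-SR alone is confirmatory. If any of the nine measures could support the claim, it is about 12% to 33% at common correlations of 0.9 to 0.3, and at most 37%. The nine-measure figures assume a separate 5% test of each named domain; the correlations are assumptions. The documents do not support saying that the primary outcome is undefined, that any one significant result counts as success, or that the error rate is 37%.

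**What to change.** Keep the Abstract's choice and carry it through:

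- In Primary objectives, keep one comparative objective: the between-arm difference in change in SCIM-SR total score from baseline to 6 weeks, tested at two-sided 5%.
- Name that score and that test in Research Hypothesis and in item d of Data Analysis, in place of the general reference to ADL.
- Move objectives c to e to Secondary objectives. State that they are reported as supportive, without confirmatory claims, or state the multiplicity method that will apply to them.
- Say in the sample-size paragraph that 90 was computed for SCIM-SR, if that is so.

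A particular testing sequence for the secondary measures is optional. The change is to wording only and leaves the sample size at 90. The cost is that the sponsor gives up claiming success on the other measures, unless it states a multiplicity method for them.

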### **Secondary objectives**

- f. To determine the significance of biographical variables (Address zone, Age, Gender, Highest level of Education, Marital status, Employment status, Monthly income, Level of SCI, Type of SCI ‘complete/incomplete’), ASIA, and Dysfunction on the progress of ADL.
- g. To measure the adherence to the intervention using the SADL-eM adherence therapist-report questionnaire which will be developed for this purpose.

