#### **Participants, sampling method, sample size, and setting**

Participants in the study will be SCI inpatients from the Gaza Strip, both genders, of any cause or type of SCI, and age 18-65 years. They will be recruited from admitted inpatients in one of the three rehabilitation settings (Hamad, ElWafa, or ElAmal Rehabilitation hospitals). Readmissions will be included in the study if they are eligible. These three inpatient rehabilitation hospitals are located in the Gaza Strip of Palestine and are private sector health services. They provide comprehensive rehabilitation services. Their rehabilitation teams include physical rehabilitation doctors, rehabilitation nurses, physiotherapists, occupational

therapists, speech therapists, clinical dietitians, psychologists, social workers, orthoptists, and community-based rehabilitation workers. The sample size was determined to detect an effect size of 15%, power of 80%, 5% margin of error, and 95% Confidence Interval (CI). The study sample of 90 SCI individuals will be randomized to two groups, conventional therapy (n1=45) and intervention/SADL-eM & conventional therapy (n2=45) using a simple randomization approach. Inclusion and exclusion criteria are listed in Box 1.

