## **Data Collection**

All admitted SCI patients will be evaluated by the research supervisor in the setting for eligibility within three days of admission to the inpatient rehabilitation setting, until the desired sample size is reached. Eligible individuals will sign a consent form and then be assigned randomly to one arm of the study by the research supervisor. The allocation sequence will be concealed from patients, therapist and, assessor. The data about exposure to the educational intervention will be collected by a separate research assistant by phone and will be concealed

from the assessor. Each occupational therapy department will assign four therapists to follow up the trial cases – two for the intervention and two for control group. All the staff in the occupational therapy department, participants, and assessors will be requested not to discuss the trial and intervention material between them. The importance of concealing any information until the end of the study will be explained. Study participants are not allowed to switch between occupational therapists or study arms. They will be asked not to participate in other educational interventions (peer or external) related to their rehabilitation or seek treatment outside their trial. The head of occupational therapy department within each rehabilitation setting will supervise participants and assigned occupational therapists in both study arms to reduce contamination bias such as sharing intervention content with the control group, sharing similar time and space of occupational therapy sessions, and exchange of therapists.

Contamination bias due to already existing background and/or receipt of additional educational interventions will be measured within each arm of the study (Chi-Square test to compare the progress means). However, no case will be eliminated from statistical analysis due to contamination bias.

The study will adopt approaches to prevent loss of participants to follow-up by making questionnaires as easy to complete as possible, providing incentives in the form of a free copy of the educational manual for the control group, and explaining the importance of the study (Magill, et al., 2019).

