The researchers will use the same outcome measures all through the study and with both of study arms. Biographical data will be collected by a research assistant once on the participant's admission and consent to participate. ADL data collection from each participant in the study will take place in a face-to-face interview twice (on admission before providing with the educational manual and 6 weeks later) using: (a) Patient-administered SCIM-SR and (b) Research assistant-administered SCIM-III, the Private Religiousness Practices Scale, Organizational Religiousness Short-Form, and the domains of ADL covered by the educational manual including driving and community mobility, personal device care, health management and maintenance, Wudu, and Salat. The data will be used to compare the results and means of both groups, answer the research question, and test the study hypothesis.

Polit, et al. (2001) pointed out that the validity of the experimental study can be threatened by history, selection, and maturation. This study finding's validity will be enhanced by concealing intervention group using a blinded assessor. The bias of sampling and contamination will be

minimized through randomization and assuring freedom of participation and anonymity of participants.

Objective data collected in clinical settings using valid and reliable tools is essential for evaluating the impact of an intervention (Polit, et al., 2001). The validity and reliability of the data collected and results of the study will be improved using standardized measurement tools such as SCIM-III and SCIM-SR.

**Biographical Data Collection Tool:** an English 24-item tool that captures demographic and socioeconomic data including age, gender, marital status, level of education, employment, monthly income, accommodation, diagnosis, and cause and type of SCI. The researchers developed the tool to be used in English version in this study.

**Spinal Cord Independence Measure-Self Reported (SCIM-SR):** a patient-reported 17-item tool that evaluates the ability of a person with SCI to perform specified activities independently, with assistance, or with assistive devices. The tool uses an ordinal scale.

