**Figure 1: Random generated numbers of intervention group**

## **Box 1: inclusion and exclusion criteria**

Inclusion criteria
▪ Confirmed SCI diagnosis by computed tomography or magnetic resonance report.
▪ ASIA: A, B, and C
▪ Age between 18 and 65 years old.
▪ Stable medical condition.
▪ Time elapsed after SCI is not more than 6 months.
▪ Minimum time of stay in inpatient rehabilitation unit is six weeks.
▪ Active involvement in rehabilitation program.
▪ Sufficient comprehension (read/write) of the Arabic language.
Exclusion criteria
▪ Unconfirmed diagnosis.
▪ Patients who have communication and/or cognitive disorders such as global aphasia and memory deficit.
▪ Patients with disturbed level of awareness such as coma or lethargy.
▪ Time elapsed since SCI is more than 6 months.
▪ ASIA: D and E
▪ Unstable medical condition.
▪ Patients who have other cause(s) of disability in addition to SCI such as stroke or amputation.
▪ Age less than 18 or more than 65 years old.
▪ Time of stay in inpatient rehabilitation unit is less than six weeks.
▪ Inactive involvement in rehabilitation program.
▪ Patients with a progressive disease or a psychiatric condition that would interfere with active participation in rehabilitation program.
▪ Patients with cardiovascular contraindications.
▪ Persons who become walking ambulatory during the inpatient period.
▪ Persons with complete tetraplegia C4 or above.
▪ Persons on mechanical ventilator.

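### Time since injury (any value up to six months) must be established at screening but enters neither the arm comparison nor objective f, costing some precision and leaving objective f open to confounding

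*Combined protocol and SAP*

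**What the plan says.** **Entry window.** Box 1 requires "Time elapsed after SCI is not more than 6 months" and repeats the limit as an exclusion. It gives no lower limit. Data Collection states: "All admitted SCI patients will be evaluated by the research supervisor in the setting for eligibility within three days of admission". The interval therefore has to be known for every patient before randomisation.

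**Why it will vary.** Time zero is admission to rehabilitation, not injury. The Introduction says that patients first complete medical management elsewhere and that "Due to limited resources, many patients are added to waiting list before admission". The participants section adds: "Readmissions will be included in the study if they are eligible".

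**Factors for progress.** Objective f begins "To determine the significance of biographical variables (Address zone, Age, Gender, Highest level of Education, Marital status, Employment status, Monthly income", continues with level and type of injury, and ends "ASIA, and Dysfunction on the progress of ADL". That makes eleven factors, none of which is time since injury.

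**The form.** The 24-item biographical tool is described as covering, among other things, "age, gender, marital status, level of education, employment, monthly income, accommodation, diagnosis, and cause and type of SCI". Date of injury is not named, but the list is introduced as an open one.

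**Analysis.** Data Analysis item d gives repeated measures ANOVA or linear mixed models for efficacy, with no covariate. Item c, the only item on biographical variables, describes univariable tests at baseline. No model is given for objective f. Allocation is by simple randomisation, 45 per arm, unstratified.

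**Maturation.** Data Collection accepts that "the validity of the experimental study can be threatened by history, selection, and maturation". The protections it names are a blinded assessor and randomisation; adjustment is not mentioned.

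**The concern.** Patients enter at different distances from injury, and the outcome is change over the next six weeks. If the rate of natural recovery depends on time since injury, two things follow.

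In the arm comparison, measuring before and after removes stable differences in level between patients but not differences in rate of change. Those remain in the residual and widen the confidence interval, although a variable that could absorb part of them is already known for each patient.

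In objective f, randomisation of the manual gives no protection, because the comparisons are between kinds of patient. If the wait before admission differs by address, income or severity, a listed factor can be credited with a difference that reflects how early after injury the patient was measured.

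**Working it through.** **1. The plan's own figure.** The stated target is 90 patients, an effect size of 15%, 80% power and 5% error. Read 15% as Cohen's f = 0.15 and assume a pre-post correlation of 0.5; the documents state neither. For the group-by-time test with two groups and m = 2 measurements, the noncentrality is f² × N × m / (1 − rho) = 0.0225 × 90 × 2 / 0.5 = 8.1 on F(1, 88). This gives power 0.804, and 90 is the smallest even N that reaches 80%. The figure is reproduced without any covariate.

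**2. Precision gained by adjustment.** Let r be the correlation of time since injury with six-week gain. The documents give no value, so a range is assumed. Adjustment multiplies the standard error by sqrt(1 − r²):

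| r | sqrt(1 − r²) | Cut in standard error |
|---|---|---|
| 0.2 | 0.980 | 2% |
| 0.3 | 0.954 | 5% |
| 0.4 | 0.917 | 8% |
| 0.5 | 0.866 | 13% |

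In power terms, divide the residual variance in step 1 by 1/(1 − R²), where R² is the share of variance in change explained, and spend one degree of freedom. At N = 90, R² of 0.05, 0.10, 0.20 and 0.30 gives power 0.823, 0.843, 0.882 and 0.920, against 0.804 unadjusted. If baseline SCIM-SR is also in the model, the relevant r is the correlation that remains after baseline is accounted for, which may be smaller.

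**3. Chance imbalance between arms.** Assume that time since injury is uniform over a window of width w months. Its SD is w / sqrt(12), and the standard error of the between-arm difference is SD × sqrt(2/45) = SD × 0.2108.

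| Assumed window | SD | SE of difference | 95% range | Chance of more than 0.5 month |
|---|---|---|---|---|
| 0 to 6 months | 1.73 | 0.365 | ±0.72 | 17% |
| 1 to 6 months | 1.44 | 0.304 | ±0.60 | 10% |
| 2 to 6 months | 1.15 | 0.243 | ±0.48 | 4% |

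This is not a second loss on top of step 2. With a linear relation, slope × SD of time = r × SD of gain. The imbalance therefore contributes r² of the variance of the unadjusted estimate, and adjustment leaves the other 1 − r². The unadjusted standard error already contains both parts.

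**4. Objective f.** Take a listed factor with no effect of its own that correlates q with time since injury. Its marginal correlation with gain is c = q × sqrt(R²). With N = 90, z = atanh(c) × sqrt(87), and the rejection rate is Phi(z − 1.96) + Phi(−z − 1.96). For R² = 0.20 and q = 0.2: c = 0.089, z = 0.84, rate 0.13.

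| q | Rate, R² = 0.10 | Rate, R² = 0.20 |
|---|---|---|
| 0 | 0.05 | 0.05 |
| 0.1 | 0.06 | 0.07 |
| 0.2 | 0.09 | 0.13 |
| 0.3 | 0.14 | 0.24 |
| 0.5 | 0.32 | 0.56 |

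The error is inflated only to the extent that q differs from zero, and the documents do not give q.

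**The case against.** The strongest reply is that a concurrent randomised control group is the standard answer to maturation. Both arms recover over the same six weeks, the estimate is unbiased in expectation, and the unadjusted interval already allows for chance imbalance. All of this stands. A reader might infer from the wide entry window that the arm comparison is biased, or that imbalance does harm beyond the stated interval. Neither follows. Adjustment here is a matter of efficiency.

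A reader might also take confounding of objective f as established. It is not. The documents give no waiting times, no rule linking the wait to address, income or severity, and no recovery slope. Confounding is plausible, not shown.

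The full 0-to-6-month spread is generous. Patients complete medical management before referral, many then wait, and Box 1 requires a stable condition, so entry close to the day of injury is unlikely. Readmitted patients must also meet the six-month limit, so they do not widen the window. The narrower windows above show the effect of this.

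Finally, the form may already record the injury date, since only part of its 24 items is described. That would lower the cost of the fix, but it would not put the variable into objective f or into any model.

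**Conclusion.** The point holds as a modest, nearly free improvement. A variable that the trial must establish for every patient is used to decide entry and then appears in no analysis. For the SCIM-SR comparison the loss is one of precision: about 2% to 13% of the standard error if the correlation with six-week gain is 0.2 to 0.5, which is an assumption. The corresponding between-arm imbalance has a 95% range of about ±0.5 month (uniform over 2 to 6 months) to ±0.7 month (uniform over 0 to 6 months); this describes the same effect. Objective f may be confounded if time since injury is related to a listed factor, and the documents allow no estimate of how much. Nothing here invalidates the trial or its primary comparison.

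**What to change.** 1. Record days from injury to admission if the 24-item form does not already do so, and tabulate it by arm.
2. Prespecify it as a continuous covariate in the SCIM-SR comparison. Use either a model of the six-week score adjusted for baseline SCIM-SR, or a covariate-by-time term in the mixed model. A main effect alone would not alter the group-by-time test.
3. Add it to objective f and write down an analysis for that objective, which Data Analysis now lacks. Estimate each listed factor's association with ADL progress adjusted for time since injury and baseline score. Fitting all the factors at once, several of them multi-category, would risk overfitting in 90 patients.

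The cost is one field if the date is not already recorded, and one degree of freedom in the arm comparison. The term should be fixed before outcome data are seen, because adding it later would look data-driven.
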